13 ETHICAL AND REGULATORY CONSIDERATIONS	
14. DISSEMINATION POLICY	
15. REFERENCES	
16. APPENDICIES	

ii. LIST OF ABBREVIATIONS

BAP1 BRCA-associated protein 1

CA Competent Authority

CAG Confidentiality Advisory Group

CI Chief Investigator
CRF Case Report Form

FEV1 Forced expiratory volume in 1 second

FISH fluorescence in situ hybridisation

GCP Good Clinical Practice

GMP Good Manufacturing Practice

ICF Informed Consent Form

ICH International Conference on Harmonisation of technical

requirements for registration of pharmaceuticals for human

use.

IHC Immunohistochemical

ISF Investigator Site File (This forms part of the TMF)

ISRCTN International Standard Randomised Controlled Trials

Number

MDT Multi-Disciplinary Team

MTAP methylthioadenosine phosphorylase

NHS R&D National Health Service Research & Development

PI Principal Investigator

PIC Participant Identification Centre
PIS Participant Information Sheet

PET-CT Positron Emission Tomography CT

PPI Patient and Public Involvement

PM Pleural Mesothelioma
QA Quality Assurance
QC Quality Control

REC Research Ethics Committee
SDV Source Data Verification

SOP Standard Operating Procedure

SSI Site Specific Information

TMF Trial Master File

TMG Trial Management Group
TSC Trial Steering Committee

iii. TRIAL SUMMARY

Trial Title	Reducing Repeat Pleural Biopsies In Suspected Cancer – a study of the TARGET trial cohort			
Internal ref. no. (or short title)	REPLICA			
Trial Design	additional diagnostic tests in no could increase the diagnosis ramalignancy. Standard pathway	A UK based multicentre study to evaluate whether performing additional diagnostic tests in non-diagnostic pleural biopsies could increase the diagnosis rate in suspected pleural malignancy. Standard pathway vs proposed (involving additional diagnostic tests) pathway		
Trial Participants	A study of the 59 participants who enrolled in the RCT TARGET study at 8 UK sites between September 2015 and September 2018. Inclusion criteria included suspicious pleural thickening on CT scan, non-diagnostic pleural biopsy and MDT decision to perform further CT-guided biopsy to pursue a diagnosis.			
Planned Sample Size	59 participants were enrolled in TARGET. Total sample size is 118, as each participant provides matched data for both standard and proposed pathways. 129 biopsy samples available in total.			
Follow up duration	12 months (already completed as part of TARGET trial)			
Planned Trial Period	12-18 months total			

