10 STATISTICS AND DATA ANALYSIS

The independent variable is the availability of BAP1, p16 FISH and MTAP testing (binary; available *vs* not available). The primary outcome is identification of malignancy on biopsy (binary; diagnostic *vs* non-diagnostic), with diagnosis defined as i) histopathological confirmation on standard testing or ii) histopathological features of PM with demonstrated BAP1, p16 or MTAP deletion or iii) Multi-disciplinary Team (MDT) diagnosis. It is assumed that confirmation of a malignant diagnosis stops the diagnostic pathway with no additional biopsies required. Any subsequent biopsies for these participants will not be included in the analysis, preventing double-counting. Secondary outcomes include total number of biopsies required, time to diagnosis, stage at diagnosis, number of MDT discussions, biopsy-associated costs, biopsy-related adverse events and survival. Potential confounding variables include age, sex, biopsy method and tumour histology and these will be adjusted for, when possible, in the analysis.

Outcome measures will be tabulated for standard and proposed pathways and compared using descriptive statistics (including the McNemar test). Univariable and multivariable logistic regression will look for an association between the availability of these tests and likelihood of a diagnostic biopsy. The relationship between secondary outcomes and availability of the tests will be evaluated using adjusted and unadjusted regression analyses and time to event analysis (cox proportional hazard model).

Sample Size:

Total number of patients: 59

Total histological samples for analysis: 129 (all participants had multiple biopsies)

REPLICA

IRAS ID 329574

Each participant will be assessed as a case (proposed pathway) and as an internal control (standard pathway) generating two groups of 59 = 118 records for inclusion in the study

Sample size is determined by the number recruited to the TARGET study which demonstrated diagnostic sensitivity (without these additional tests) of 30%. A sample size of 118 (59 in each arm) will allow detection of an increased diagnostic rate of 60% with 95% confidence intervals of +/- 8.8% (based on BAP1 loss prevalence of 60%).

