On the assumption that the combination of BAP1 and MTAP will increase the diagnostic rate still higher, a sample size of 118 will allow detection of an increased diagnostic rate of 70% with 95% confidence intervals of +/- 8.2% and a diagnostic rate of 80% with 95% CI of 7.2%

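### The stated precision treats 59 participants as 118 independent observations, so all three planned 95% confidence interval half-widths are too small by a factor of about 1.4

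*Protocol*

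**What the plan says.** The Sample Size part of section 10 gives the number of people plainly: "Total number of patients: 59". It then explains that each is assessed as a case and as an internal control, "generating two groups of 59 = 118 records for inclusion in the study". The trial summary (Planned Sample Size) says the same: "Total sample size is 118, as each participant provides matched data for both standard and proposed pathways".

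Section 10 acknowledges that the size was fixed by recruitment to TARGET, where the diagnostic sensitivity without the extra tests was 30%. It supports that size with three precision statements. The first begins "A sample size of 118 (59 in each arm") and claims that this "will allow detection of an increased diagnostic rate of 60% with 95% confidence intervals of +/- 8.8" points. The second reads "a sample size of 118 will allow detection of an increased diagnostic rate of 70% with 95% confidence intervals of +/- 8.2" points. The third gives 7.2 points for a rate of 80%. No power calculation is given.

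**The concern.** A confidence interval for a proportion depends on the number of independent people in whom that proportion is observed. The increased rates of 60%, 70% and 80% are rates with the additional tests available, and 59 records describe them. The other 59 records are the same people under standard testing, where the stated rate is 30%. Adding them to the denominator doubles the apparent sample without adding any information about the rate in question.

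These half-widths are the only quantitative support the protocol offers for its size. They also suggest a resolution the study does not have. The protocol distinguishes 60% (BAP1 alone) from 70% and 80% (assumed with MTAP added). With the stated 8.2 points, an observed 70% would exclude both neighbouring scenarios; with the width that 59 people give, it would exclude neither.

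**Working it through.** **Inputs**, all from section 10: 59 participants; 118 matched records (2 × 59); 95% confidence, taken as two-sided with z = 1.96; assumed rates of 60%, 70% and 80%; standard-pathway rate of 30%.

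**Step 1. Reproduce the stated figures.** The half-width for a single proportion is 1.96 × √(p(1−p)/n). With n = 118:

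- 60%: 1.96 × √(0.24/118) = 8.84 points (stated 8.8)
- 70%: 1.96 × √(0.21/118) = 8.27 points (stated 8.2, which matches if truncated; it rounds to 8.3)
- 80%: 1.96 × √(0.16/118) = 7.22 points (stated 7.2)

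Solving the other way, n = 1.96² × p(1−p)/(half-width)² gives 119.1, 120.0 and 118.6. All are within 2 of 118, the number the text itself names.

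**Step 2. Use the number of people who supply the rate.** With n = 59:

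| Rate | Stated half-width | Half-width, n = 59 | Ratio |
|---|---|---|---|
| 60% | 8.8 | 1.96 × √(0.24/59) = 12.50 | 1.42 |
| 70% | 8.2 | 1.96 × √(0.21/59) = 11.69 | 1.43 |
| 80% | 7.2 | 1.96 × √(0.16/59) = 10.21 | 1.42 |

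The ratio is √2 = 1.414, apart from rounding in the stated figures.

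**Step 3. Try other methods with n = 59.** Results at 60%, 70% and 80%:

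- Wilson: 12.1, 11.4 and 10.1 points
- Clopper-Pearson: 13.1, 12.3 and 10.9 points
- 90% instead of 95% interval: 10.5, 9.8 and 8.6 points

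None comes near 8.8, 8.2 and 7.2.

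**Step 4. Try the paired difference as the target.** For 59 pairs the half-width is 1.96 × √((b + c − (b − c)²)/59), where b is the proportion diagnosed only by the proposed pathway and c the proportion diagnosed only by the standard pathway.

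- If no standard-pathway diagnosis is lost (c = 0, b = 0.3, 0.4, 0.5): √(0.21/59), √(0.24/59) and √(0.25/59), each times 1.96, give 11.7, 12.5 and 12.8 points.
- If the paired results are uncorrelated: 17.1, 16.5 and 15.5 points.

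This reading does not give the stated figures either.

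**Step 5. What the intervals can separate.**

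- Observed 70%: 61.8 to 78.2% as stated; 58.3 to 81.7% with n = 59, which contains both 60% and 80%.
- Observed 60%: 51.2 to 68.8% as stated; 47.5 to 72.5% with n = 59, which contains 50% and 70% but still excludes 30%.

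**Step 6. Loss of material (illustration only).** Section 2.1 warns that some samples may be too small to stain and mentions another study with under 10% of samples missing. Assuming that about 10% of participants were lost here (59 × 0.9 ≈ 53), the half-widths would be 13.2, 12.3 and 10.8 points.

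**The case against.** The strongest counter-argument is that nothing in the conduct of the study depends on these widths. TARGET recruitment fixed the size, the cohort is complete, and no test or endpoint changes when the figures are corrected. The protocol is open about the matching, and the McNemar test it names respects the pairing. The main contrast is also not in danger. For 30% against 60% in 59 pairs, about 18 discordant pairs all in one direction gives an exact p below 0.0001. Even if the paired results were uncorrelated (an assumption; about 25 against 7 discordant pairs), p is about 0.002. All of this stands. It limits the consequence and makes correction cheap, but it does not make the stated widths true.

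A second argument is that the protocol names no interval method, so the formula in step 1 is inferred. A Clopper-Pearson interval with n = 129, the number of biopsies, gives 8.76, 8.22 and 7.24 points and so rounds to all three stated figures. The inference should be acknowledged as such. But the text names 118, not 129, and 129 biopsies from 59 people are not independent observations either. Section 10 itself drops biopsies taken after a diagnosis, so as not to count people twice. Under either reading the denominator exceeds the number of people.

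It is also fair to say that the 53-participant illustration rests on thin ground: the source figure is an upper bound, counts samples rather than people, and comes from a different study. The conclusion does not depend on it.

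**Conclusion.** The precision statement is wrong as written. All three half-widths in section 10 use the number of records where the number of people is needed. They should be 12.5, 11.7 and 10.2 points at 60%, 70% and 80%, instead of 8.8, 8.2 and 7.2. This assumes that all 59 participants are evaluable and uses the usual normal approximation; an exact method or any loss of samples widens the intervals further. The error lies in the anticipated precision, not in the planned McNemar comparison, and an increase from 30% to 60% remains detectable. What is lost is the claim that the study can resolve the diagnostic rate to within 7 to 9 points and so tell its own scenarios apart.

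**What to change.** - In section 10 and in the trial summary, state the sample size as 59 participants, each contributing one matched pair. If 118 is kept at all, it should appear only as a count of records and never as the basis for an interval.
- Replace 8.8, 8.2 and 7.2 with 12.5, 11.7 and 10.2 points, or give exact intervals: for example, 35/59 = 59%, 95% CI 46 to 72% (Clopper-Pearson 45.7 to 71.9%). Name the method used.
- Describe the figures as the expected precision of the diagnostic rate, not as what the study can detect.
- Preferably, add the precision for the paired difference from 30%, stating the assumed discordance: 11.7, 12.5 and 12.8 points if no standard-pathway diagnosis is lost.
- Note that these widths assume all 59 have sufficient stored material, as section 6 requires for inclusion.

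The cost is an amendment to protocol wording and a less favourable stated precision. No further patients, samples or tests are needed, and the planned analysis need not change on this account.

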11 DATA MANAGEMENT

Anonymised data from the TARGET trial will be extracted and stored in an excel workbook. Lab data will be shared by the lab team in this format. All data, including identifiable data needed to access clinical information will be stored securely on NBT systems.

All essential documents will be retained in accordance with North Bristol NHS Trust's Archiving SOP following the end of a study.

12 MONITORING, AUDIT & INSPECTION

None planned

13 ETHICAL AND REGULATORY CONSIDERATIONS

13.1 Research Ethics Committee (REC) review & reports

Before the start of the trial, approval will be sought from a REC for the trial protocol, and other relevant documents.

13.2 Peer review

The study proposal has been reviewed by Southmead Hospital Charity and NBT Research Sponsor as part of the funding application process.

13.3 Public and Patient Involvement

In research design:

This project centres around improving the patient diagnostic experience so patients and their carers are integral to the design. Feedback from PPI representatives included narrative descriptions of their personal experiences of the diagnostic process, and how delays have impacted their journeys. They have voiced support for "anything that could improve things, as it's a very stressful time".

Our dedicated PPI group, consisting of patients with mesothelioma, their carers and a MesoUK nurse. met on 13/3/23 and with [name] on 13/11/23. There were extensive discussions about the study design with feedback welcomed from the group. All responders thought felt this research could be useful, supporting and changes in practice that could help future patients. They highlighted the importance of reducing total number of biopsies and time taken to diagnosis, both of which have been included as secondary outcomes. All respondents reported they would be happy for their data and samples to be used in this context, without the need for prior consent.

PPI representatives also reviewed the plain English summary, which was amended in response to their comments and feedback.

In research management:

We have identified a willing patient representative to sit on the project management group. He will contribute to study oversight, be involved in discussions around data analysis and contribute to write

up as an author on the final manuscript. He will be invited to assist with dissemination of results to other PPI partners.

In Dissemination of findings:

Results will be relayed to those through the PPI process so far who have indicated they wish to stay informed. I will create a plain English summary of the findings to ensure accessibility, sharing these with patients and carers via our local mesothelioma patient group and the annual mesothelioma patient and carer conference. We will disseminate results to the public via the Bristol Academic Respiratory and UK pleural Society twitter feeds, through the Meso UK newsletter and Southmead Hospital Charity updates.

13.4 Regulatory Compliance

The study will not commence until a Favourable REC opinion has been received and HRA approval has been granted.

Approval will also be sought from a Confidential Advisory Group (CAG) to access identifiable patient information while processing patient samples, so findings can be linked with clinical outcomes.

13.5 Protocol compliance

Protocol non-compliances are departures from the approved protocol.

- accidental protocol deviations can happen at any time. They must be adequately
 documented on the relevant forms and reported to the Chief Investigator and Sponsor
 immediately.
- deviations from the protocol which are found to frequently recur are not acceptable, will require immediate action and could potentially be classified as a serious breach.
- See RI/QMS/SOP/012: R&I Managing Breaches of GCP or the Protocol

13.6 Notification of Serious Breaches to GCP and/or the protocol

A "serious breach" is a breach which is likely to effect to a significant degree -

- (a) the safety or physical or mental integrity of the participants of the trial; or
- (b) the scientific value of the trial
- the sponsor will be notified immediately of any case where the above definition applies during the trial conduct phase
- the sponsor of a clinical trial will notify the licensing authority in writing of any serious breach of
 - (a) the conditions and principles of GCP in connection with that trial; or
 - (b) the protocol relating to that trial, as amended from time to time, within 7 days of becoming aware of that breach
- See RI/QMS/SOP/012: R&I Managing Breaches of GCP or the Protocol

13.7 Access to data, data protection and patient confidentiality

All study documents will be stored securely in an access-restricted environment, accessible only to study staff and authorised personnel. Data will be collected and stored in accordance with the Data Protection Act 1998. Participants' personal data will be treated as strictly confidential. Anonymity of participants will be upheld by recording only participants' study number, initials and date of birth on key study documentation and analysis files. Only authorised study team members will have access to participants' personal data where this is necessary to link participants to their clinical records on clinical systems and for sample retrieval. No study information will be routinely shared with any external third parties. For the purposes of specific analyses, linked anonymised data may be shared. Only data required for each specific analysis will be shared. Any data being shared externally will be transferred securely electronically with password protection.

13.8 Financial and other competing interests for the chief investigator, PIs at each site and committee members for the overall trial management n/a

13.9 Indemnity

This is an NHS-sponsored research study. For NHS sponsored research HSG(96)48 reference no.2 refers. If there is negligent harm during the clinical trial when the NHS body owes a duty of care to the person harmed, NHS indemnity covers NHS staff, medical academic staff with honorary contracts, and those conducting the trial. NHS indemnity does not offer no-fault compensation and is unable to agree in advance to pay compensation for non-negligent harm.

13.10 Amendments

See RI/QMS/SOP/003: Research Study Amendments

14 DISSEMINIATION POLICY

14.1 Dissemination policy

The results of this research will be disseminated to patients and carers, fellow mesothelioma researchers and clinicians. Patients will be informed via our local mesothelioma patient group and the annual mesothelioma patient and carer conference. We will disseminate the results to the public via the Bristol Academic Respiratory and UK pleural Society twitter feeds. We will present results to fellow academics at scientific conferences. Clinicians will be informed via the UK Pleural Society state-of-the-art meetings and/or annual update day. The final report will be written up for publication in a peer-reviewed scientific journal, published open-access.

14.2 Authorship eligibility guidelines and any intended use of professional writers

Authorship of any papers produced from this study will be determined by The International Committee of Medical Journal Editors authorship criteria.

TARGET Consent form Version 3.0 21/10/2016

Amendment No.	Protocol version no.	Date issued	Author(s) of changes	Details of changes made

List details of all protocol amendments here whenever a new version of the protocol is produced. Protocol amendments must be submitted to the Sponsor for approval prior to submission to the REC committee or MHRA.
